NMES uses a lightweight, battery powered electrical stimulation unit (which is attached to the patient via self-adhesive electrodes) to produce a controlled contraction of the underlying muscle. It can be self-administered at home while the participant is passively sitting or lying down thus decreasing the demands of exercise while still allowing the participant many of the same benefits.²⁴ Previous studies using NMES and those with HF have shown benefit, but, the protocols have varied widely, the outcome variables of interest have also varied widely, in addition there was no further formal exercise program encouraged upon completion of the study. The innovation of this study is that all the previous knowledge gained has been merged into a protocol that is double blinded, patient centered protocol to improve compliance, tolerability, and ease of use. Also, this proposal focuses on NMES being used as the stepping stone to enable those with HF to participate in structured exercise program.

Section 2: Rationale and Specific Aims Research Design and Methods

The purpose of this double blinded, randomized, controlled, longitudinal study is to determine if NMES will increase muscle mass and strength, decrease sedentary time, and improve HF symptoms and exercise capacity, thus improving quality of life in patients with HF. It is hypothesized that with this increase in muscle mass, patients will improve overall exercise tolerance and capacity. In addition, after the intervention patients will be better able to tolerate an exercise program thus improving adherence to exercise recommendations. After 6 weeks of intervention, patients will be encouraged to participate in a formalized exercise program.

Specific Aim 1: Test the effect of NMES on muscle mass and strength in patients with HF. We will use DXA and dynamometer to evaluate this aim. We hypothesize that NMES will increase lean muscle mass and decrease fat mass of the thighs. Also that strength and force of the thighs will improve.

Specific Aim 2: Evaluate the effect of NMES on exercise capacity and activity in patients with HF. We will use 6-minute walk test to evaluate exercise capacity and ActivePal accelerometer to evaluate activity levels. We hypothesize that exercise capacity and the amount of daily activity will increase while sitting/lying time will decrease from pre intervention to post intervention time points.

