Data analysis will be done using SPSS, v. 22; an alpha level of .05 will be used for all tests except where noted. Study measures will be examined using univariate statistics, including means, standard deviations and frequency distributions, and graphical techniques, such as box plots and histograms. Distributions for continuous outcome measures will also be examined for violations of normality using normal probability plots. If there is evidence of lack of normality for a particular outcome, transformations (e.g., logarithmic) will be used so that the distribution of the transformed variable more closely approximates normality. The analysis strategy to be used to test all aims is repeated measures analysis of variance (ANOVA). Each ANOVA model will include the main effects of Time (baseline, 6 weeks, 6 months' post intervention period) and Group (intervention and sham intervention), as well as the Time by Group

interaction. Post-hoc pairwise comparisons of means will be done using Fisher least significant difference procedure. The repeated measures models will be estimated using the MIXED procedure in SAS. This analysis will: **test the effect of NMES on muscle mass and strength in those with HF (Aim 1); evaluate the effect of NMES on exercise capacity and activity (Aim 2); and assess the effect of NMES on HF symptoms and quality of life (QOL); and finally, evaluate the effect of NMES on enrollment and utilization of a formalized exercise program (aim 4).** There will be a separate model for each outcome variable, and the significance of the main and interaction effects will indicate the effect of the intervention over time.

Power Considerations

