With at least 27 subjects per group (treatment and sham) completing the study and an alpha level of .05, the ANOVA F test will have approximately 97% power to detect a significant main or interaction effect, assuming a large effect size, and a modest degree of correlation among observations from the same individual. A large effect size in this context is one such that the ratio of the standard deviation of the means to the standard deviation of the observations within the populations is at least 0.4.⁷⁷ In addition, the ANOVA F tests will have at least 69% power to detect main effects and 95% power to detect an interaction effect, with alpha set at .05 and at least a medium effect size (i.e., ratio of standard deviation of means to standard deviation of observations within populations is at least 0.25). Given that we expect a large effect between the groups for many outcomes, in addition to the estimated power of at least 95% for the detection of a Group by Time effect in the presence of a medium to large effect, the sample size chosen for this exploratory study will provide sufficient power to detect this significant group differences over time with a high probability; in addition, this study will allow us to more precisely measure expected power in order to plan future studies.

Section 9: Privacy and Confidentiality Issues

Patients' confidentiality will be preserved by coding each data sheet with a unique subject number, and storing the code number key in a locked file cabinet in a locked research office located in the School of Nursing. Protection against breach of confidentiality is provided by training all individuals involved in the research process about the necessity for complete confidentiality, housing all data collected in locked file cabinets in an access-restricted area, and by use of password protected computers and secure servers. Most data are collected using the REDcap system, and any additional files will be stored in Box Health on IU Servers. Although there can be no absolute guarantee of confidentiality, every practical precaution will be taken.

Section 10: Follow-up and Record Retention

Study recruitment will be ongoing. The duration of the entire study is expected to be 18 months, while each participants expected duration is 6 months. The de-identified data will be retained on computer files indefinitely. Hard copy study documents will be kept in a locked, file cabinet in a locked room. Electronic study information will be stored

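### No lead outcome or between-group contrast is named for any aim, while every outcome is tested at .05 and either a main effect or an interaction counts as evidence

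*Combined protocol and SAP*

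**What the plan says.** Section 2 sets four specific aims with directional hypotheses. Aim 1, for example, is to "Test the effect of NMES on muscle mass and strength in patients with HF". Section 5 tags most of the main instruments with the aim they serve, then adds further repeated measures that belong to no stated aim.

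Under Statistical Analysis in Section 8:

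- The significance level: "an alpha level of .05 will be used for all tests except where noted". No exception is noted.
- The number of models: "There will be a separate model for each outcome variable".
- What counts as evidence: "the significance of the main and interaction effects will indicate the effect of the intervention over time". The models contain Time, Group and Time by Group.
- Follow-up tests: "Post-hoc pairwise comparisons of means will be done using Fisher least significant difference procedure".

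The Power Considerations paragraph starts from "With at least 27 subjects per group (treatment and sham) completing the study". It gives power for a main or interaction effect, names no outcome, expects large effects on many outcomes, and calls the study exploratory. Nowhere is an outcome, visit or contrast called primary, and no multiplicity procedure is described.

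**The concern.** An aim with several scores, each open to more than one test at .05, has no single answer. If one score is significant and the others are not, the plan does not say whether the aim was met. The analyst chooses after seeing the data, and the nominal 5% does not describe the error rate of that choice.

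The rule on main effects makes this worse. A Time main effect is change common to both groups, so it says nothing about NMES against sham. A Group main effect averages over all three visits, including baseline, before anyone has been treated. Only a between-group difference in change addresses the hypotheses, yet the plan lets any of the three terms count.

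Section 2 says that the data will support an application for a larger grant. A positive result picked from many could therefore fix the outcome and the assumed effect of the next trial.

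**Working it through.** **1. The plan's own figures.** The plan states no familywise error rate. Its stated numbers are power figures: about 97% (f = 0.4, main or interaction), 69% (f = 0.25, main) and 95% (f = 0.25, interaction). Inputs are N = 54, m = 3 visits and alpha .05. The within-person correlation is called modest without a number, so I assume rho = 0.31.

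- Group effect: lambda = f² x N x m / (1 + (m − 1) x rho), df 1, 52. For f = 0.4: 0.16 x 162 / 1.62 = 16.0, power 97.5%. For f = 0.25: 0.0625 x 162 / 1.62 = 6.25, power 68.9%.
- Interaction: lambda = f² x N x m / (1 − rho), df 2, 104. For f = 0.25: 0.0625 x 162 / 0.69 = 14.7, power 93.2%.

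All three agree within 2 points. They describe one test on one unnamed outcome at .05.

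**2. Counting outcomes.** This is my count from the scores and subscales that Sections 2 and 5 describe.

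- Aim 1: thigh lean mass, thigh fat mass, strength, torque = 4.
- Aim 2: 6-minute walk; ActivPal sitting/lying, standing, moving, steps = 5.
- Aim 3: three MSAS-HF subscales; MLHFQ total, physical, emotional = 6.
- Aim 4: enrolment, utilisation = 2.
- Tied to aims: 4 + 5 + 6 + 2 = 17.
- Others: PROMIS Fatigue 1, self-efficacy 1, outcome expectations 2, sit-to-stand 1, timed up and go 1, self-care index 1, Brief Pain Inventory 2, PHQ-8 1 = 10. Total 27.
- Low count: one score for each of the six aim-tagged instruments (DXA, dynamometer, 6-minute walk, ActivPal, MSAS-HF, MLHFQ) plus one for Aim 4 = 7.

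**3. Chance of at least one significant result if NMES affects nothing.** For k independent tests this is 1 − 0.95^k. For correlated outcomes I simulated equally correlated test statistics. The documents give no between-outcome correlations, so 0, 0.3 and 0.5 are assumptions.

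| Scores | Tests per score | 0 | 0.3 | 0.5 |
|---|---|---|---|---|
| 27, all | 1 | 75% | 63% | 48% |
| 17, aim-linked | 1 | 58% | 49% | 38% |
| 17, aim-linked | Group and Group x Time | 83% | 73% | 62% |
| 7, low count | 1 | 30% | 27% | 23% |

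Check on the third row: the two tests use different error terms, so the chance is roughly 1 − (1 − p)², with p from the row above. That gives 1 − 0.42² = 0.82, 1 − 0.51² = 0.74 and 1 − 0.62² = 0.62. The simulated entries are good to two or three points.

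**4. Within one aim** (independent, one test per outcome): Aim 1, 1 − 0.95^4 = 19%; Aim 2, 1 − 0.95^5 = 23%; Aim 3, 1 − 0.95^6 = 26%; Aim 4, 1 − 0.95^2 = 10%. A single outcome with Group and Group x Time both counted also gives 1 − 0.95^2 = 10%.

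**5. Not counted.** The Time test is left out. So are the LSD comparisons: 2 groups x 3 visits = 6 cells, hence up to 15 pairs per outcome. LSD does not control error across that many pairs.

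**The case against.** The strongest reply is that this is a small preparatory study. It calls itself exploratory, says it will help to plan future studies, and feeds a grant application. Strict familywise control across four distinct aims is then partly a matter of preference. That stands, and it is why Holm is only an option below. It does not excuse the rule itself: the same plan sets out to determine whether NMES works, states a directional hypothesis for each aim and reads significance as the answer.

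A second reply is that the plan is not silent on structure. Instruments are tied to aims, Aim 2 speaks of change from before to after the intervention, and the sample-size argument leans chiefly on the Group by Time effect. This stands too, and it narrows the gap. What is missing is a ranking within each aim and a fixed between-group contrast. Aim 2's wording describes change over time, not a difference between groups.

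A reader might go further and infer that some 25 outcomes are all formally tested, so that a chance finding is more likely than not. The documents do not support that as a flat statement. They give no count, do not say that every subscale gets a model, and name only Aims 1-4 as what the analysis will test. The claim also requires no true effect on any outcome. With one test per score it fails for the 17 aim-linked scores at a correlation of about 0.3 (49%), and even for all 27 at 0.5 (48%). Several scores are parts of one instrument, so some correlation is certain.

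**Conclusion.** The concern holds as a flaw in the decision rule. Followed as written, the plan exceeds 5% within every aim, by a factor of about two to five (10% to 26%) on the independent, one-test basis. Across the aim-linked scores, the chance of at least one false positive runs from about 38% to 83%, depending on the correlation and on whether one or both Group-related tests count. The low count of 7 scores with one test each brings it to 23% to 30%, still well above 5%.

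All of these figures assume no effect of NMES on any outcome, my reading of which scores are outcomes, and assumed between-outcome correlations. They should be quoted as a range with those conditions. The absence of a lead outcome and contrast depends on none of them. It should be settled before analysis.

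**What to change.** Before any analysis by group, add to Section 8:

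1. One lead outcome per aim from what the aims already list, for example thigh lean mass, 6-minute walk distance, MLHFQ total and enrolment in a formal exercise programme. The table of variables in Section 5 has no row for enrolment, so its definition must be written too.
2. One contrast per aim, for example the NMES-minus-sham difference in change from baseline at 6 weeks, and the group difference at the final visit for Aim 4.
3. A statement that only this contrast answers the aim, and that the Time and Group main effects do not.
4. All other outcomes and pairwise comparisons reported with 95% confidence intervals as exploratory.

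This needs no new data, visits or participants. It holds 5% for each aim's lead claim. Across four unadjusted lead tests the chance of any false positive is still 1 − 0.95^4 = 19% if they are independent.

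Holm across the four would hold that at or below 5%, but this is optional and its cost should be stated. At the first step, .05 / 4 = .0125. With rho = 0.31, power for the medium-effect interaction falls from 93% to 83%. For a simple 6-week two-group comparison with 27 per group (noncentrality d x √(27/2), df 52), power falls from 82% to 64% at d = 0.8 and from 44% to 24% at d = 0.5, before any gain from baseline adjustment.

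If a single-visit contrast becomes the lead, the figures under Power Considerations no longer apply, with or without Holm, and must be restated for that contrast.

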The research associate will review all data collected for completeness and readability, correcting any errors prior to data analysis. We will collect "reason for drop out" if a participant stops the study. We will continue to try to schedule subsequent data collection interviews even if the participant is not able to complete a previous one. During each data collection session, team members will work with participants to encourage response to all items and will review data to ensure all data points are completed unless the participant prefers not to answer. Nonetheless, missing data will occur and this will be acknowledged in the analysis.⁷⁶ We will conduct initial analyses using the maximum likelihood approach, as it emphasizes the use of all available data. The use of random effects modeling techniques, in particular repeated measures mixed modeling, allows for missing data by adjusting the estimation process to account for bias resulting from data missing at random. Baseline data from those with and without missing data will be compared to determine whether there are systematic differences, using demographic and personal variables. If the data are not amenable to the maximum likelihood method random effects analysis, multiple imputation will be used as an alternative procedure for handling missing data. Multiple imputation produces results similar to maximum likelihood when used under identical conditions. We will use multiple imputation in the sensitivity analyses; this will allow for the comparison of study results under a variety of assumptions to assess the robustness of the findings.

Statistical Analysis

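### The within-person covariance model is not specified, and the wording points to one common correlation, which would make the 6-week change contrast conservative and the final-visit change contrast anti-conservative if correlations fall with time

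*Combined protocol and SAP*

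**What the plan says.** Four parts of the combined protocol and SAP bear on the error term.

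- **Section 8, Statistical Analysis:** "The analysis strategy to be used to test all aims is repeated measures analysis of variance (ANOVA"). Time has three categories, with Group and the Time by Group interaction, and there is a separate model for each outcome. Then: "Post-hoc pairwise comparisons of means will be done using Fisher least significant difference procedure". The models are to be estimated in SAS MIXED, although SPSS v. 22 is named as the analysis software in the same paragraph. Also, "an alpha level of .05 will be used for all tests except where noted".
- **Section 8, Missing Data:** maximum likelihood on all available data, with "The use of random effects modeling techniques, in particular repeated measures mixed modeling".
- **Section 8, Power Considerations:** "With at least 27 subjects per group (treatment and sham) completing the study and an alpha level of .05", power is given for the ANOVA F tests under "a modest degree of correlation among observations from the same individual".
- **Section 5, NMES Protocol Summary:** measures are repeated after the 6-week intervention. The sham arm is then offered active treatment, all participants are encouraged to start an exercise programme, and a last visit follows 3 months after the intervention. The Section 5 table of variables and Section 8 label that visit 6 months. The two timings must be reconciled.

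No section names a covariance structure, a degrees-of-freedom method, a sphericity check, the error term for LSD, or whether LSD depends on a significant F test.

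**The concern.** Classical repeated measures ANOVA, and equally a random-intercept model, assumes equal variances and the same correlation between every pair of visits. It judges every within-person contrast against one pooled error. That assumption is doubtful here. Baseline and post-treatment are 6 weeks apart, whereas the last visit comes months later, after the exercise advice and the offer of active treatment to the sham arm. Baseline is likely to correlate more strongly with 6 weeks than with the last visit, and the final variance may be larger.

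If so, the pooled error is too large for the 6-week change and too small for the final change. The 6-week difference in change is the direct test of the stimulation and matches the pre-to-post hypothesis in Specific Aim 2. It would lose power, while final-visit claims would have intervals that are too narrow. An unstated structure also leaves room to choose one after seeing the data, across many outcome models.

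**Working it through.** **Inputs.** From the plan: 27 completers per arm (54 in total), three visits, alpha .05, f = 0.40 ("ratio of the standard deviation of the means to the standard deviation of the observations within the populations is at least 0.4") and f = 0.25 ("ratio of standard deviation of means to standard deviation of observations within populations is at least 0.25"). The plan gives no numerical correlation, so every correlation below, and the 0.4 SD effect, is an assumption.

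**1. The plan's own power.** With one common correlation ρ:
- Group: λ = f²·54·3/(1+2ρ), df 1 and 52.
- Interaction: λ = f²·54·3/(1−ρ), df 2 and 104.

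At ρ = 0.32 this gives 97.4% (Group, f = 0.40), 68.4% (Group, f = 0.25) and 93.6% (interaction, f = 0.25). The plan states 97%, 69% and 95%. All three agree within 2 points for ρ of 0.31 to 0.34, so the sample size is consistent with a common-correlation model.

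**2. Pooled against own standard error.** With equal SDs (set to 1), the between-arm difference in change has own SE = √(2(1−r)·2/27), where r is the correlation for that pair of visits. The pooled SE replaces r by the mean correlation r̄, so pooled SE / own SE = √((1−r̄)/(1−r)).

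For .85/.70/.65 (0–6 wk / 6 wk–final / 0–final), r̄ = .733:
- 6 weeks: own SE 0.149, pooled SE 0.199, ratio √(.267/.15) = 1.33.
- Final: own SE 0.228, pooled SE 0.199, ratio √(.267/.35) = 0.87.

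The critical t on 104 df is 1.98. The pooled test therefore rejects at 1.98 × 1.33 = 2.64 own SEs at 6 weeks (normal approximation, two-sided 0.8%) and at 1.98 × 0.87 = 1.73 own SEs at the final visit (8.3%).

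Power at 6 weeks for 0.4 SD: the pooled cut-off is 1.98 × 0.199 = 0.394, and (0.394 − 0.4)/0.149 = −0.04, or about 52%. With its own SE (t on 52 df, 2.01) the cut-off is 0.299, and (0.299 − 0.4)/0.149 = −0.68, or about 75%.

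**3. Simulation** (27 per arm, complete data, LSD not gated; repeat runs differ by about a point or less):

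| Assumed correlations | SE ratio, 6 wk / final | Type I, 6 wk | Type I, final | 6-wk power for 0.4 SD, pooled vs own |
|---|---|---|---|---|
| .85/.70/.65 | 1.33 / 0.87 | 0.9% | 8.7% | 52% vs 74% |
| same, final SD 20% larger | 1.47 / 0.86 | 0.4% | 9.3% | 42% vs 76% |
| .80/.60/.50 | 1.35 / 0.86 | 0.9% | 9.5% | 37% vs 63% |
| .80/.75/.70 | 1.12 / 0.91 | 2.9% | 7.2% | 55% vs 63% |
| .40/.30/.25 | 1.07 / 0.95 | 3.6% | 6.2% | 22% vs 26% |
| all .50 | 1 / 1 | about 5% | about 5% | 31% vs 30% |

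With an unstructured covariance both contrasts reject at about 5% in every decay case tried.

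**4. LSD gated on the interaction F.** Under a full null, final-visit error drops to about 3% to 5%. When a real 6-week effect exists the gate opens more often, and final-visit error is about 5% to 9% (7.7% for .85/.70/.65). Gating also lowers 6-week power further, to 42% against 75% for .85/.70/.65.

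**5. The interaction F itself.** Pooled, it rejects 5.8% of the time under the null for .85/.70/.65. Its power for a 0.4 SD effect at 6 weeks only is 54%, against 74% with an unstructured covariance.

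**The case against.** A reader might infer that the plan commits to a single pooled error and that its error bars are therefore wrong. The documents do not support that. No section states compound symmetry, and SAS MIXED, which is named, allows an unstructured covariance under which nothing goes wrong. The correlation in the power section is a planning simplification and does not bind the analysis.

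A reader might also blame the unequal spacing of visits. Time enters as categories, so spacing alone does no harm; unequal correlations or variances are needed.

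Three further points stand in part.

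- **The correlations are assumed.** The stated power implies about 0.31 to 0.34, and decay around that level gives only modest distortion (the .40/.30/.25 row). Higher values are plausible for some outcomes, but the plan gives no 6-week correlations.
- **LSD may be meant in its protected form.** That removes the final-visit excess under a full null, but not when a 6-week effect exists, and it does not restore 6-week power.
- **Pairwise comparisons of means may mean arm against arm at one visit.** With equal variances these are unaffected (4.7% to 5.1% under a common-correlation fit in the decay cases). But the planned interaction and the pre-to-post hypothesis concern change, where the problem arises.

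The plan also calls the study exploratory, which lowers the stakes. It is nevertheless meant to support a grant application and the planning of later studies, so its standard errors matter.

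**Conclusion.** The point holds as a gap in specification that is cheap to close. It is not an error that the documents prove. The wording permits, and most naturally implies, a common-correlation fit. If that fit is used and correlations fall with time or the final variance differs, the 6-week change contrast is conservative (type I error about 0.4% to 3.6%) and the final-visit change contrast is anti-conservative (about 6% to 10% ungated).

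The loss of 6-week power for 0.4 SD runs from 4 points at low correlations, through 8 under mild decay, to 22 for .85/.70/.65, and is larger still in the more extreme rows of the table. These sizes rest on assumed correlations, complete data and 27 per arm. With equal variances and equal correlations the concern disappears.

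**What to change.** State in Section 8 that each continuous outcome will be fitted in MIXED with an unstructured 3x3 within-person covariance, REML and Kenward-Roger degrees of freedom. Estimate the between-arm difference in change from baseline at 6 weeks (the main test) and at the final visit as model contrasts, each with its own standard error, in place of pooled-error LSD comparisons. REML still uses all available data, so this fits the Missing Data section. In the same edit, reconcile SPSS with SAS and the 3-month with the 6-month label for the final visit.

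Cost: about one sentence of wording for the model, and 6 covariance parameters instead of 2, which 54 participants with three visits can support. If correlations turn out equal, about 1 point of power is lost (30% against 31% in the all-.50 case).

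### The plan lets a Time effect shared by both arms count as evidence for NMES and follows it with unadjusted Fisher LSD on unspecified means with no stated gate

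*Combined protocol and SAP*

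**What the plan says.** Section 8, Statistical Analysis, fits one repeated-measures model per outcome, with Time at three levels, Group at two levels and their interaction. On follow-up tests it says only that "Post-hoc pairwise comparisons of means will be done using Fisher least significant difference procedure". The significance level is general: "an alpha level of .05 will be used for all tests except where noted". No multiplicity adjustment is noted. For interpretation, "the significance of the main and interaction effects will indicate the effect of the intervention over time".

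The section does not state whether the compared means are the three Time means, the two Group means or the six Group-by-Time cells. Nor does it state which F test, if any, must be significant before LSD is applied.

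Three other places bear on the point. Section 2 (importance of the knowledge to be gained) expects participants in either arm to benefit from a formal exercise program. The NMES Protocol Summary in Section 5 has participants encouraged to start one before the final visit. Specific Aim 2 words its hypothesis as change from before to after the intervention. Power Considerations calls the study exploratory.

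**The concern.** There are two linked problems.

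First, a Time main effect measures change averaged over both arms. Practice on the walk and strength tests, recovery after a recent admission, or taking up exercise can all produce it with no NMES effect. A rule that reads main effects as the effect of the intervention allows a significant Time test to be reported as benefit.

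Second, Fisher LSD is a set of unadjusted t tests. Its only protection is a preceding F test. With three means and their own F test, that protection is adequate. With six cells it is not: a shared trend can make the Time F significant, and the arm comparisons that follow are then unprotected. Pre-post tests within each arm are opened in the same way, and significance in one arm only is easily misread as an arm difference.

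At stake is a reported NMES benefit at some visit, for some outcome, when the arms do not differ. Section 2 says that the data will support a larger grant application, so such a result would carry forward.

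**Working it through.** **Inputs from the documents.** Two arms, three visits, alpha .05, and the sample size: "With at least 27 subjects per group (treatment and sham) completing the study and an alpha level of .05". So N = 54 and m = 3.

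**Inputs assumed.** The within-person correlation (rho) is described only as modest. The size of a shared trend is not given; I take a linear rise of 0, 0.3, 0.5 or 0.8 SD from baseline to the final visit. Pairwise tests are two-sided, with compound symmetry.

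**Step 1: reproduce the plan's power, to fix rho.** The plan states 97% for f = 0.4, and 69% (main effects) and 95% (interaction) for f = 0.25.

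- Between-group: lambda = f² × N × m / (1 + 2 rho), df 1 and 52. At rho 0.32 and f = 0.4: 0.16 × 162 / 1.64 = 15.80, power 97.4%. At f = 0.25: 0.0625 × 162 / 1.64 = 6.17, power 68.4%.
- Interaction: lambda = f² × N × m / (1 − rho), df 2 and 104. At f = 0.25: 10.125 / 0.68 = 14.89, power 93.6%.

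All three stated figures are matched within 2 points for rho 0.31 to 0.34, so about 0.33 is the plan's implied value. I also use 0.7 as a higher correlation.

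**Step 2: false arm differences per outcome.** I simulated the 2 × 3 design with no Group and no interaction effect. Same-visit arm comparisons were LSD t tests with model-based variance and Satterthwaite df. In the table, any significant F (Group, Time or interaction) opens them.

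| rho | Shared rise (SD) | Time F significant | False difference, either post-baseline visit | Any of three visits |
|---|---|---|---|---|
| 0.32 | 0 | 4.9% | 5.3% | 7.2% |
| 0.32 | 0.3 | 36.8% | 6.7% | 9.5% |
| 0.32 | 0.5 | 80.1% | 8.7% | 12.3% |
| 0.32 | 0.8 | 99.6% | 9.5% | 13.5% |
| 0.7 | 0 | 5.0% | 5.3% | 6.3% |
| 0.7 | 0.3 | 71.0% | 7.4% | 9.6% |
| 0.7 | 0.5 | 99.1% | 8.3% | 10.8% |
| 0.7 | 0.8 | 100% | 8.2% | 10.8% |

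Other gates, whatever the trend:

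- No gate: 9.4-9.5% (rho 0.32) or 8.2-8.4% (rho 0.7) at the two post-baseline visits. The ceilings under independence are 1 − 0.95² = 9.75% for two visits and 1 − 0.95³ = 14.26% for three.
- Interaction F as gate: about 2.1% at the post-baseline visits and 3.1% at any visit (rho 0.32). Over rho 0 to 0.9 the any-visit rate is 0.8% to 4.3%.
- Each single comparison stays at about 5% throughout.

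**Step 3: significant change in exactly one arm.** If each arm's pre-post test has probability p of significance, exactly one is significant with probability about 2p(1 − p), which cannot exceed 50%. The standard error of one arm's change, in SD units, is √(2(1 − rho)/27). At rho 0.33 it is √(1.34/27) = 0.223. Under a linear rise, half has occurred by 6 weeks.

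- Rise of 0.8 SD: 0.40/0.223 = 1.80, p about 0.43, and 2 × 0.43 × 0.57 = 49%.
- Rise of 0.3 SD: 0.15/0.223 = 0.67, p about 0.10, and 2 × 0.10 × 0.90 = 18%. Requiring some F to be significant first brings this to about 13%.

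The baseline-to-6-week range is therefore about 13-49%, against about 4% with no trend and the same gate. It does not apply to every contrast. When the change is large enough that both arms are nearly certain to be significant, the rate falls. For baseline to final visit at 0.8 SD and rho 0.7, the ratio is 0.8/√(0.6/27) = 5.4 and the rate is about 0.1%.

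**The case against.** The strongest reply is that the plan never says a Time effect opens arm comparisons, nor that six cells are compared. On an ordinary reading, each F test opens only its own means. A Time effect then opens the three Time means, where LSD holds the familywise error, and arm comparisons within a visit need the interaction F. The rate then stays below 5% and no trend can raise it. This is correct as arithmetic, but nothing in the Statistical Analysis section commits to that reading. The sentence on interpretation points the other way by placing main effects beside the interaction.

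Three stronger readings are tempting, and the documents do not support them.

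- A reader might infer that false arm differences roughly double. Over shared rises of 0.3 to 0.5 SD at rho 0.32, the three-visit rate goes from 7.2% to 9.5-12.3%, or 1.3 to 1.7 times. It approaches double (13.5/7.2 = 1.9) only at 0.8 SD. The three-visit figure also counts baseline, which is measured before randomization, and a chance difference there is not a false NMES benefit.
- A reader might infer that the trend is always the cause. If LSD is run with no gate, the inflation is the same with or without a trend.
- A reader might infer that the plan will claim benefit from a change in one arm only. Aim 2's pre-to-post wording invites this, but no such rule is written.

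The exploratory label also counts. It tempers the seriousness of a modest familywise excess. It does not make a shared Time effect informative about NMES.

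**Conclusion.** The concern holds as a fault in the decision rule, with a moderate and conditional numerical effect. The part that rests on the text alone is that a significant Time effect may be taken to indicate the intervention effect, and that LSD is specified without its means or its gate.

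The numbers depend on how those gaps are filled. If any significant F including Time, or no gate, opens the within-visit arm comparisons, the chance per outcome of at least one false post-baseline arm difference is about 7-10% rather than 5%, or 9-14% counting baseline. This assumes 27 per arm, rho about 0.33 to 0.7 and a shared rise of 0.3 to 0.8 SD. At rho 0.9 with no protection left, the figures are 7.0% and 8.3%. The error of a single comparison is unaffected. Under the same assumptions, one-arm-only significance from baseline to 6 weeks arises in about 13-49% of trials with no arm difference, so within-arm results cannot serve as evidence. The trend sizes are assumptions: the protocol makes a shared change plausible but gives no magnitude.

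**What to change.** Replace the LSD sentence and the interpretation sentence in Statistical Analysis. State that the intervention effect for each outcome is judged by the Time by Group interaction or by two prespecified between-arm contrasts from the mixed model, at 6 weeks and at the final visit. State that the Time main effect and within-arm changes are descriptive only.

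Then choose one control for the two contrasts:

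- **Interaction gate.** Test them only after a significant Time by Group F. With no arm difference, a shared rise of 0.8 SD and rho 0.32, the chance of a false difference at either visit is 2.1%.
- **Holm adjustment.** With no true arm difference, Holm has the same chance of any false claim as Bonferroni, which gives 4.9% in that setting.
- **Fixed order.** Test 6 weeks first, and the final visit only if 6 weeks is significant. Simulated error was 4.7% to 5.3% whatever the trend.

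The change is a few sentences and needs no extra participants or data. The cost is fewer pairwise comparisons to report and slightly less power per contrast. Fixed order has a further cost: a final-visit effect, for example one that emerges after participants take up formal exercise, could not be claimed unless the 6-week contrast is significant. If a late effect is of real interest, the interaction gate or Holm is the better choice.
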